9.1. Statistical Hypotheses

The primary clinical efficacy hypothesis is that vibegron + pharmacological therapy is more effective than placebo + pharmacological therapy in reducing both a) the mean daily micturition episodes and b) mean daily urgency episodes, based on a 3-day diary.

9.2. Sample Size Determination

Approximately 1088 subjects will be randomized in a 1:1 ratio to receive one of the following study treatments:

- Vibegron 75 mg tablet (N = 544)
- Matching placebo tablet (N = 544)

Approximately 544 subjects each will be assigned to the vibegron and placebo treatment groups. Assuming a total of 15% of subjects will discontinue prior to Week 12 (for any reason), there will be approximately 462 evaluable subjects in the vibegron and placebo treatment groups (924 subjects total) at the end of Week 12. The study has approximately 94.3% power to detect a between-group treatment difference of 0.46 in change from baseline in micturitions at a 2-sided 0.05 level assuming a variability estimate of 1.972 based on vibegron Study MRK-008 data and the FDA's statistical reviewer of mirabegron NDA data showing that the micturition treatment effect in men taking 50 mg of mirabegron is 70% of the overall 50 mg of mirabegron population. Additional details are provided at the end of this section.

For the second co-primary endpoint, 462 evaluable subjects per treatment group has approximately 90% power to detect a between-group treatment difference of 0.60 in change from baseline in urgency episodes at a 2-sided 0.05 level assuming a variability estimate of 2.811 based on vibegron Study MRK-008 data and the FDA's statistical reviewer of mirabegron NDA data. Additional details are provided at the end of this section.

The overall study power will be more than 84% with the co-primary endpoints based on the Bonferroni inequality (ie, for any events A and B, $P(A \cap B) \geq P(A) + P(B) - 1$).

Derivation of Estimated Treatment Effect in Men

Based on the published results of the Phase 2 trial of mirabegron and the FDA statistical reviewer of the OAB NDA, we estimated the following:

- The Phase 3 results will have at least 85% of the treatment difference of the Phase 2 results
- The treatment difference for men is at least 70% of the effect of the general OAB population

Table 3 summarizes this information and sources.

Table 3. Data and Sources Supporting Study Sample Size Calculations

Mirabegron Results			
	N	PBO Adj CFB	
Study	Overall	Men	Overall
178-CL-046	473	133	-0.6
178-CL-047	425	116	-0.61
		Simple Average	-0.61

	Phase 2 Micturition PBO Adj CFB	Phase 3 Micturition PBO Adj CFB	Phase 3 as a % of Phase 2
Comparing Phase 3 to Phase 2	-0.64	-0.605	94.5%

Merck 008 Results and Ph 3 Projections			
Measure	Vib 50mg	Vib 100mg	SD
Micturition	-0.64	-0.91	1.972
Urgency Episodes	-0.76	-1.24	2.811

Midpoint between 50mg and 100mg	Micturition	Urgency Episodes
Ph 2 Projected Effect of 75mg	-0.78	-1.00
Ph 3 Projected Effect of 75mg	-0.66	-0.85
Ph 3 Projected Effect of 75mg in Men	-0.46	-0.60

Power in Baseline BPH Treatment Subgroups:

Although this study will not formally test the treatment effect in subgroups by baseline BPH treatments, it is sufficiently sized to estimate treatment differences within these subgroups. Assuming that approximately half of the subjects are on alpha blockers alone and half on alpha blockers plus 5-ARI, then approximately 544 subjects will be randomized to each subgroup with 462 evaluable (231 per arm). Using the above assumptions with a two-sided test with a type-I error of 0.10, each subgroup will have 97.1% power for micturitions and 94.5% power for urgency episodes. Assuming that the endpoints and subgroups are independent, then the power for each subgroup to be significant on both endpoints is 91.7%, and the power for both subgroups to be significant on both endpoints is 84.0%.

The impact of imbalances in 5-ARI plus alpha blockers versus alpha blockers alone will be monitored and controlled if needed.

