1.2.4.1. Power in Baseline BPH Treatment Subgroups

Although this study will not formally test the treatment effect in subgroups by baseline BPH treatments, it is sufficiently sized to estimate treatment differences within these subgroups. Assuming that approximately half of the subjects are on alpha blockers alone and half on alpha blockers plus 5-ARI per stratified randomization, then approximately 544 subjects will be randomized to each subgroup with 462 evaluable (231 per arm). Using the above assumptions with a two-sided test with a type-I error of 0.10, each subgroup will have 97.1% power for micturition episodes and 94.5% power for urgency episodes. Assuming that the endpoints and subgroups are independent, then the power for each subgroup to be significant on both endpoints is 91.7%, and the power for both subgroups to show significant treatment difference on both endpoints is 84.0%.

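### Subgroup power by baseline BPH treatment is overstated: 231 per arm gives about 80%, 74%, 60% and 36%, not 97.1%, 94.5%, 91.7% and 84.0%

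*Protocol*

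**What the plan says.** Under Power in Baseline BPH Treatment Subgroups, Protocol 9.2 says there will be no formal subgroup tests but that the trial is large enough to estimate treatment differences within these subgroups. The supporting argument runs as follows.

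- Split: "Assuming that approximately half of the subjects are on alpha blockers alone and half on alpha blockers plus 5-ARI".
- Size: "approximately 544 subjects will be randomized to each subgroup with 462 evaluable (231 per arm").
- Test: "Using the above assumptions with a two-sided test with a type-I error of 0.10".
- Result for single endpoints: "each subgroup will have 97.1% power for micturitions and 94.5% power for urgency episodes".
- Joint results, treating endpoints and subgroups as independent: 91.7% for both endpoints in one subgroup, and "the power for both subgroups to be significant on both endpoints is 84.0" per cent.

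SAP 1.2.4.1 repeats the same sizes and all four figures ("each subgroup will have 97.1% power for micturition episodes and 94.5% power for urgency episodes"). SAP section 9, which lists departures from the protocol's analysis, does not revise them.

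**The concern.** A simple comparison raises the question. At the same assumed effects and SDs, the plan gives the whole trial 94.3% and 90% power with 462 per arm, yet gives a subgroup half that size 97.1% and 94.5%. The subgroup calculation relaxes alpha from 0.05 to 0.10, but that does not make up for halving the sample.

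What is at stake is how the subgroup results will be read. SAP 6.1.3 puts alpha blocker use with or without 5-ARI first among the subgroups to be modelled for the co-primary endpoints, and plans a forest plot of 95% intervals with a reference line at zero. A reader who believes each subgroup has well over 90% power would take an interval that crosses zero as evidence of no effect in that subgroup. At the power the design actually has, such a result is a fairly common chance outcome even when the assumed effect is fully present.

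**Working it through.** **Inputs** (Protocol 9.2; SAP 1.2.4 and 1.2.4.1 agree)

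- Micturitions: the study is powered "to detect a between-group treatment difference of 0.46 in change from baseline in micturitions at a 2-sided 0.05 level". So δ = 0.46, and the SD given there is 1.972.
- Urgency: δ = 0.60, SD = 2.811.
- 1:1 allocation with 15% dropout: 544 × 0.85 = 462.4, so 462 evaluable per arm in the whole trial. Half of these in each subgroup gives 231 per arm.
- Alpha: two-sided 0.05 for the whole trial, two-sided 0.10 for the subgroups.

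**Formula.** With n per arm, SE = SD × √(2/n), and power ≈ Φ(δ/SE − z), where z = 1.960 (two-sided 0.05) or 1.645 (two-sided 0.10). The noncentral t with 2n − 2 degrees of freedom is the exact version.

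**Step 1: reproduce the whole-trial power (462 per arm, two-sided 0.05).**

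- Micturitions: SE = 1.972 × √(2/462) = 0.1297; 0.46/0.1297 = 3.545; Φ(3.545 − 1.960) = 94.4% (t: 94.3%). The plan says 94.3%.
- Urgency: SE = 2.811 × √(2/462) = 0.1850; 0.60/0.1850 = 3.244; Φ(3.244 − 1.960) = 90.0% (t: 90.0%). The plan says 90%.

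The method and inputs are therefore the plan's own.

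**Step 2: subgroup power as described (231 per arm, two-sided 0.10).**

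- Micturitions: SE = 1.972 × √(2/231) = 0.1835; 0.46/0.1835 = 2.507; Φ(2.507 − 1.645) = 80.6% (t: 80.5%).
- Urgency: SE = 2.811 × √(2/231) = 0.2616; 0.60/0.2616 = 2.294; Φ(2.294 − 1.645) = 74.2% (t: 74.1%).
- Both endpoints in one subgroup, independent: 0.8047 × 0.7408 = 59.6%.
- Both endpoints in both subgroups: 0.596² = 35.5%.

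**Step 3: find what reproduces the printed figures** (noncentral t, two-sided 0.10).

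| Case | Micturitions | Urgency | Both, one subgroup | Both, both subgroups |
|---|---|---|---|---|
| Printed | 97.1% | 94.5% | 91.7% | 84.0% |
| 231 per arm, 0.46/0.60 | 80.5% | 74.1% | 59.6% | 35.5% |
| 462 per arm, 0.46/0.60 | 97.1% | 94.5% | 91.8% | 84.2% |
| 231 per arm, 0.66/0.85 | 97.4% | 94.5% | 92.1% | 84.8% |

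Solving back for n from the printed 97.1% and 94.5% gives 461 and 462 per arm. The joint figures then agree with the printed ones up to rounding: 0.971 × 0.945 = 0.9176, and 0.917² = 0.841.

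**Step 4: try other readings of the test at 231 per arm.** One-sided 0.10 gives 89% and 84%. One-sided 0.20 gives 95.2% and 92.7%. Neither recovers the printed values.

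**Step 5: precision of the planned display.** The 95% half-widths at 231 per arm are 1.96 × 0.1835 = 0.36 and 1.96 × 0.2616 = 0.51. If the assumed effects are real, a subgroup's interval excludes zero about 71% of the time for micturitions and 63% for urgency (noncentral t, two-sided 0.05: 70.6% and 62.9%).

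**The case against.** The arithmetic cannot be defended. The case on the other side is about weight, cause and remedy.

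- **Weight.** The subgroups lie outside the alpha-controlled testing sequence, Protocol 9.4.4.1 makes subgroup analyses optional, and SAP 6.1.3 reports the interaction estimate and p-value, not a within-subgroup verdict at 0.10. No decision rule, sample size or patient procedure depends on the four figures. This stands, and it limits the consequence to interpretation.
- **Chance of a miss.** On a single endpoint in a single subgroup, a miss occurs in about 20% to 26% of trials, which is not the likely outcome. That is fair. But at least one endpoint is missed in a given subgroup about 40% of the time (1 − 0.596), and somewhere across the two subgroups about 64% of the time (1 − 0.355).
- **Cause.** The documents show no calculation, so the use of 462 per arm is an inference. Using the projected effects before the 70% reduction for men (0.66 and 0.85) with 231 per arm also comes within one point of every printed figure. It fits less well, conflicts with the statement that the preceding assumptions apply, and conflicts with the footnote to SAP Table 1 marking the row for men as the one used for sizing. Under either explanation the printed power does not belong to 231 per arm with 0.46 and 0.60.
- **Independence.** The 60% and 36% inherit that assumption. With the same single-endpoint powers, joint power in one subgroup can lie anywhere from 0.805 + 0.741 − 1 = 55% to 74%. Squaring gives about 30% to 55% for both subgroups. Even the upper ends are far below 91.7% and 84.0%.
- **Estimation versus testing.** The plan claims adequacy for estimation, and half-widths of 0.36 and 0.51 are smaller than the assumed effects. Whether that is enough is a judgement, but the plan rests it on power figures that are wrong.

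**Conclusion.** The concern holds. The stated subgroup power is too high by about 17 points for micturitions, 20 for urgency, 32 for both endpoints in one subgroup and 48 for both endpoints in both subgroups. The corrected values rest on the plan's planning effects and SDs, 15% dropout, an equal split between the two BPH treatments, two-sided alpha 0.10 and, for the joint figures, independence. An unequal split would lower power further in the smaller subgroup. That 462 was entered as the per-arm size is the best-fitting explanation but is not documented. The co-primary powers, the overall power above 84% and the total of 1088 are not affected.

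**What to change.** In Protocol 9.2 and SAP 1.2.4.1, replace the four figures with about 80% (micturitions), 74% (urgency), 60% (both endpoints in one subgroup) and 36% (both endpoints in both subgroups). State that they assume 231 per arm, two-sided alpha 0.10, an equal split and, for the last two, independence. Replace the claim of adequate size with a statement that the subgroup results are estimates with limited power; giving the expected 95% half-widths (about 0.36 and 0.51) would make this concrete. The change is to wording only. Enrolment, randomisation and the planned analyses stay as they are, and the sponsor's only cost is a less favourable statement of subgroup power.

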9.3. Populations for Analyses

Analysis Populations

Screened Set

The Screened Set consists of all subjects who are screened for the study. This population is used primarily for subject accounting purposes and will generally not be used for summary or analysis.

Run-in Set

The Run-in set consists of all subjects who entered the run-in period of the study. Subjects will be considered run-in failures if they enter the run-in period but are not randomized to receive double-blind medication.

Randomized Set

The Randomized Set consists of all subjects who are randomized to receive study medication regardless of whether they take a dose.

Safety Analysis Set (SAF)

The Safety Analysis Set consists of all subjects who receive at least one dose of double-blind study medication. Subjects will be classified according to the treatment they actually received.

Full Analysis Set (FAS)

The Full Analysis Set (FAS) population will serve as the primary population for the analysis of efficacy data in this trial. Since the endpoints related to incontinence only apply to subjects who meet the definition of incontinence at trial entry, it is necessary to have a separate FAS definition with an additional criterion to define the primary analysis population for incontinence endpoints.

FAS consists of all randomized subjects who took at least one dose of double-blind study medication and have at least one evaluable change from baseline micturition measurement. Subjects will be analyzed according to their randomized treatment, irrespective of premature discontinuation, according to the Intent-to-Treat (ITT) principle.

Full Analysis Set for Incontinence(FAS-I)

FAS-I consists of all randomized subjects with incontinence at baseline who took at least one dose of double-blind study medication, have an evaluable baseline urgency urinary incontinence measurement, and have at least one evaluable change from baseline urgency urinary incontinence measurement.

Note that “subjects with incontinence at baseline” are defined as meeting the following criteria:

- An average of ≥ 8.0 micturitions per Diary Day
- An average of ≥ 1.0 urinary incontinence episodes per Diary Day

Per-Protocol Set (PPS) and Per-Protocol Set for Incontinence (PPS-I)

The PPS and PPS-I exclude patients from the FAS and FAS-I due to important protocol deviations that may substantially affect the results of the efficacy endpoints (ie, major protocol deviations associated with efficacy). The final determination on protocol deviations, and thereby the composition of the PPS and PPS-I, will be made prior to the unblinding of the database

A supportive analysis using the PPS and PPS-I will be performed for the co-primary efficacy and secondary endpoints. Subjects will be included in the treatment group to which they are randomized, regardless of which treatment actually received, for the analyses of efficacy data using the PPS and PPS-I.

9.4. Statistical Analyses

The statistical analysis plan (SAP) will be developed and finalized before database lock and will describe the subject populations to be included in the analyses, and procedures for accounting for missing, unused, and spurious data. This section is a summary of the planned statistical analyses of the primary and secondary endpoints.

9.4.1. Demographic and Other Baseline Characteristics

All demographic data such as age, race, and ethnicity and baseline characteristic data will be summarized by treatment group for the FAS. Subject disposition will be summarized using Screened Set.

Descriptions of medical history findings will be coded using the latest Medical Dictionary for Regulatory Activities (MedDRA) version. Medical history may be summarized in the descending order of overall frequency, by system organ class and preferred term.

Prior and concomitant medications will be coded using the latest version of World Health Organization (WHO) Drug Dictionary. The number and percentage of subjects receiving prior or concomitant medications will be summarized by treatment group.

Baseline prostate volume, Qmax, IPSS, and PVR will be summarized. Baseline disease characteristics related to primary and secondary variables will be summarized under primary and/or secondary efficacy analyses.

9.4.2. Efficacy Analyses

All statistical tests will be 2-sided hypothesis tests performed at the 5% level of significance for main effects. All confidence intervals will be 2-sided 95% confidence intervals, unless stated otherwise.

9.4.2.1. Analysis Endpoints

The primary and secondary efficacy endpoints are listed below and analyses will be defined in the following sections. All analyses for other efficacy/effectiveness and safety endpoints listed below will be defined in the SAP.

Co-Primary Efficacy Endpoints

- CFB at Week 12 in the average number of micturition episodes per day
- CFB at Week 12 in the average number of urgency episodes (urgency: need to urinate immediately) per day

Secondary Efficacy Endpoints

- CFB at Week 12 in the average number of nocturia episodes per night
- CFB at Week 12 in the average number of urge urinary incontinence episodes per day for subjects with urinary incontinence at baseline
- CFB at Week 12 in the IPSS Storage score (1-week recall)
- CFB at Week 12 in the average volume voided per micturition

9.4.2.2. Primary Analyses

For the analysis of the first co-primary endpoint (change from baseline in the average daily number of micturition episodes at Week 12), a mixed model for repeated measure (MMRM) with restricted maximum likelihood estimation will be used. The analysis model for the efficacy endpoint will include terms for treatment, visit, baseline micturition score, alpha blocker use (yes or no), baseline urinary incontinence (yes or no), region (US vs non-US), and interaction of visit by treatment. An unstructured covariance matrix will be used to model the correlation among repeated measurements. The Kenward-Roger adjustment for denominator degrees of freedom will be used with restricted (or residual) maximum likelihood (REML) to make statistical inference.

For the analysis of the second co-primary endpoint (change from baseline in the average daily number of urgency episodes at Week 12), a similar MMRM model will be used. The analysis model for the efficacy endpoint will include terms for treatment, visit, baseline score, baseline average micturition episodes per day (≤ 12 vs > 12), alpha blocker use with or without 5-ARI (yes or no), baseline urinary incontinence (yes or no), region (US vs non-US), and interaction of visit by treatment.

Other change from baseline endpoints will be analyzed using the same MMRM model as urgency episodes.

9.4.2.3. Secondary Analyses

If the null hypothesis is rejected for both co-primary endpoints, then the secondary efficacy endpoints will be tested using a fixed-sequence testing procedure until a two-sided p-value ≥ 0.05 is observed. The fixed-sequence testing procedure controls the family-wise error rate at a 2-sided alpha level of 0.05. The order of the secondary efficacy endpoints is as specified in [Section 9.4.2.1](#).

9.4.3. Safety Analyses

The safety analysis will be performed using the Safety Analysis Set and will be fully defined in the SAP. The safety parameters will include AEs and clinical laboratory and vital sign, parameters. For each safety parameter of the clinical laboratory and vital sign parameters, the last nonmissing safety assessment before the first dose of study drug will be used as the baseline for all analyses of that safety parameter.

9.4.3.1. Adverse Events

An AE will be considered a treatment-emergent AE (TEAE) if:

- The AE began on or after the date of the first dose of study drug; or

- The AE was present before the date of the first dose of study drug, but increased in severity or became serious on or after the date of the first dose of study drug

An AE that occurs more than 5 days after the last dose of study drug will not be counted as a TEAE.

An AE will be considered a treatment-emergent SAE (TESAE) if it is a TEAE that additionally meets any SAE criteria.

AEs will be coded using the latest version of MedDRA. An overall summary table of AEs by treatment group will be presented with number and percentage of subjects. The incidence of all TEAEs by primary SOC and PT will be prepared for all TEAEs, TESAEs, treatment-related TEAEs/TESAEs, TEAEs leading to discontinuation from study treatment and all TEAEs by maximum intensity. All AEs will be listed. The number and percentage of subjects with AEs of special interest, as defined in [Section 8.4.6](#), will be summarized by treatment group.

9.4.3.2. Clinical Laboratory Assessments

All continuous safety laboratory parameters will be summarized descriptively by absolute value at each visit by treatment group, together with the corresponding changes from baseline.

Laboratory reference ranges will be used to identify abnormalities with low, normal, or high values.

9.4.3.3. Vital Signs

Descriptive statistics of observed values and change from baseline for vital signs will be presented for each treatment group by visit.

9.4.3.4. Urodynamics

Descriptive statistics of observed values at Baseline and Week 12, and the change from baseline at Week 12 for the following urodynamic parameters will be presented for each treatment group by visit:

- Instilled volume at first involuntary detrusor contraction (Vol@1st IDC) (mL)
- Corrected maximum detrusor pressure during the first involuntary detrusor contraction (P_{det}@1st IDC) (cmH₂O)
- Corrected maximum cystometric capacity (MCC) (mL)
- Corrected maximum detrusor pressure during the storage phase (P_{det}@Max Storage) (cmH₂O)
- Peak flow rate during voiding (Q_{Max}) (mL/s)

- Corrected detrusor pressure at peak flow rate ($P_{det}@Q_{Max}$) (cmH₂O)
- Voided volume (VV) (mL)

This analysis will only apply to the sub-study in Part 2.

9.4.4. Other Analyses

Response efficacy endpoints will be analyzed using the Cochran-Mantel-Haenszel risk difference estimate. Missing Week 12 data will be analyzed using multiple imputation. For each imputed dataset, the estimated difference in the proportion of responders and 95% confidence interval for the difference will be calculated using the Cochran-Mantel-Haenszel risk difference estimate stratified by baseline average micturition episodes per day (≤ 12 vs > 12) and alpha blocker use with or without 5-ARI (yes or no) with weights proposed by Greenland and Robins.

9.4.4.1. Subgroup Analyses

Subgroup analyses of primary and secondary endpoints may be conducted. These may include analysis by alpha blocker use with or without 5-ARI (yes or no), baseline urinary incontinence (yes or no), and region (US vs non-US).

Sub-study may need to have a separate demographic and baseline characteristics analyses together with the urodynamic analysis to assess the effects of vibegron treatment on urodynamic parameters.

9.5. Interim Analyses

There are no interim analyses planned for this study.

